10.5 Method and Administration of Randomization

Randomized permuted blocks will be employed to obtain balanced randomization sequences for the two groups. The PI will be blinded to the randomization sequence and communicated to a designated pharmacist who not involved in clinical management of participants in order to preserve the double-blind design. The randomization assignment of participants will be carried out by this pharmacist

10.6 Intervention Visit Procedures

Prior to administration of the study compounds, participants will complete self-report questionnaires, urine testing, and clinical assessments. They will subsequently complete a 10-minute mindfulness-based psychological relaxation exercise and fill out a questionnaire regarding their study goals. Participant will be asked to disinfect their shoulder using an alcohol wipe, and the study physician will then administer the medication by intramuscular administration into the participant's deltoid muscle. Vital signs will be monitored prior to treatment, and at 45 and 90 minutes post-treatment, and blood oxygen levels will be continuously monitored using pulse oximetry. If during the post-administration observation period, ketamine administration causes an increase in systolic or diastolic blood pressure >30 mm Hg from baseline, or an increase in pulse rate >30 bpm from baseline, the measurements should be repeated after the patient has been in a resting position for 10 minutes. If the criterion is still met, then that patient will not receive further administration of ketamine and will be withdrawn from the study. After completion of the injection, participants will be monitored for 120 minutes, during which time they will undergo debriefing and complete assessments of their perceptual experience of the intervention. We will evaluate the effects of a twice weekly interventions for 4 weeks, and monitor outcomes over an additional 4-week follow-up period to inform pharmacotherapy frequency in future clinical trials. Follow-up visits may be conducted by telehealth.

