1.3 Purpose and Objectives of the Study

The primary objective of the proposed study is to directly address this critical need by preliminarily testing the efficacy of ketamine in reducing opioid use and depression symptoms among individuals (N=30) with concurrent OUD and MDD who have failed to maintain abstinence despite treatment with a standard of care pharmacotherapy for OUD (i.e. buprenorphine, methadone or naltrexone). Effects on related symptoms and psychiatric conditions (e.g., cravings, motivation to quit, and anxiety symptoms) will also be explored. To accomplish this, we will use an intent-to-treat, double-blind, randomized clinical trial to compare the efficacy of ketamine to placebo control over a twice-weekly treatment schedule for four weeks. We will examine standardized, repeated dependent measures of clinical outcomes at baseline and multiple time points after the first treatment (48h to 8 weeks post initial treatment) with primary outcomes assessed at one month following the first treatment.

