Results from several meta-analyses indicate that ketamine can induce ultra-rapid improvements in depression and suicidality (Han et. al., 2016; Wilkinson et. al., 2017). This remission is most enduring in individuals with a family history of substance use disorders (Niciu et al., 2014). It is widely accepted that all currently approved pharmacotherapy classes for depression (serotonin reuptake inhibitors, monoamine oxidase inhibitors, and tricyclic antidepressants) are associated with a delayed onset of anti-depressant activity of 2-4 weeks. A meta-analysis of nine high-quality studies showed that ketamine was significantly more effective than placebo in reducing symptoms of major depressive disorder at 24 hours, 72 hours, and 7 days post-infusion (Han et. al., 2016). Additionally, results from a recent meta-analysis of ten clinical trials showed accumulating evidence that ketamine can significantly reduce suicidal ideation within 24 hours with moderate to large effect sizes (Wilkinson et. al., 2017). The overall duration of anti-depressant response was found to last between 3-12 days (Andrade, 2017). However, in a subgroup analysis, positive family history of alcoholism was found to be associated with a significantly longer duration of anti-depressant efficacy, averaging 17 days for the family history positive group and 3.6 days for the family history negative group (Niciu et. al., 2014). This suggests that the genetics underlying substance use confer a stronger response to the effects of ketamine.

Clinical Trials for Substance Use Disorder Treatment

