3.4 Placebo Drug, Dose and Mode of Administration

A visually identical sterile saline control injection of equal volume will be also administered intramuscularly.

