4.2 Secondary Outcomes

Secondary outcomes will include changes in depression severity (as measured on the Montgomery– Asberg Depression Rating Scale), which will be calculated as a change from baseline to 4-week followup.

Montgomery Asberg Depression Rating Scale (MADRS; Montgomery, 1979). The MADRS is a clinician administered, 10-item questionnaire of depression severity. The total score ranges from 0-60, with scores of 0-6 considered normal (non-depressed), 7-19 indicative of mild depression, 20-34 indicative of moderate depression, and 35-60 indicative of severe depression. Individuals scoring 20 or higher on the MADRS will be included in the study. The MADRS evaluates the following symptoms of depression: 1) clinical appearance of sadness, 2) self-reported sadness, 3) inner tension, 4) reduced sleep, 5) reduced appetite, 6) concentration difficulties, 7) lassitude, 8) inability to feel, 9) pessimistic thought process, and 10) thoughts of suicide. The MADRS has a sensitivity of 94% and a specificity of 83%, has been shown to have high internal consistency, and correlates well with other measures of depression such as the Hamilton Depression Scale.

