12.0 DATA MANAGEMENT

12.1 Data Analysis Plan

Baseline demographic characteristics will be collected and descriptive statistics will be used to characterize participants. Data will be collected and managed using the secure REDCap (Research Electronic Data Capture) database. Descriptive statistics for primary outcomes will include 1) the percentage of individuals completing informed consent out of the number of individuals eligible on the

initial screening and 2) the percentage of individuals that complete informed consent which complete the full protocol. Other descriptive statistics for the sample population will be analyzed, and baseline characteristics that are found to be significantly associated with other outcome measures will be included as covariates. Spaghetti plots will be produced to guide modeling outcomes as a function of time. All analyses will be conducted based on intention to treat. Subjects assigned to Group B (placebo) who complete Study Wk4 (at which time main outcomes are assessed), may choose to receive 8 ketamine treatments before completing follow-up visits. To preserve study blinding, subjects who are among the final 6 subjects being enrolled will not be unblinded until primary outcomes are assessed for all 30 subjects.

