The primary dependent variables in all three analyses will be intervention group (ketamine or placebo), time (number of days), and the interaction between the two. Main hypothesis of interest will be the interaction and the post-hoc comparison at the one month after the first intervention. We anticipate the study population to include participants that are currently on antidepressants as well as those that are not. We considered stratifying randomization by this variable, however since the proporption of participants on antidepressants at baseline is expected to be small, this will be considered as an independent variable in the statistical analysis. To account for within subject correlations, several structures, such as spatial autocorrelation (to accommodate unequal time points), and AR(1) symmetry, will be examined. Diagnostics will be considered. An arcsine square root transformation may be considered to stabilize variance of the proportions. In all of the analyses, covariates will be considered to examine mediations. In a secondary analysis based on the spaghetti plots, we will consider linear and non-linear models of outcomes as a function of time. Specifically, over the 8-week follow-up period, we will examine if there exists a threshold point in time where the effect of ketamine plateaus. To achieve this, treating the joint-point as unknown, we will fit segmented regression models using non-linear mixed models.

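### Section 10.6 ends study participation as well as injections after a persistent blood-pressure or pulse rise, so endpoint MADRS and opioid-use data are lost avoidably and probably mainly in the ketamine arm

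*Combined protocol and SAP*

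**What the plan says.** Section 10.6 (Intervention Visit Procedures) has systolic pressure, diastolic pressure or pulse re-measured after ten minutes' rest if any has risen by more than 30 units from baseline. If the criterion is still met, "that patient will not receive further administration of ketamine and will be withdrawn from the study". The Table 2 footnote repeats only the re-measurement step. Section 14.0 gives withdrawn participants referrals and mentions no further assessment. The contents list an entry 12.1.2 on missing data, but the body as available has no text under it.

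On the analysis, section 1.3 states: "we will use an intent-to-treat, double-blind, randomized clinical trial to compare the efficacy of ketamine to placebo control". Section 12.1 adds: "All analyses will be conducted based on intention to treat".

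The endpoint visit is described in three ways. Section 12.1 ties the main outcomes to participants who "complete Study Wk4 (at which time main outcomes are assessed". Section 12.2 names "the post-hoc comparison at the one month after the first intervention". Section 4.2 defines the MADRS outcome as "a change from baseline to 4-week followup", a label that Table 2 places at week 8.

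The control is described in section 3.4: "A visually identical sterile saline control injection of equal volume".

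**The concern.** The rule joins two decisions. Stopping injections is a safety matter and is not questioned. Ending study participation is a data decision, and its trigger is an effect of the active drug. Section 15.2 calls a transient blood-pressure rise the most clinically significant physical adverse event of ketamine, and a saline injection would not be expected to produce it as often. Missing outcomes caused this way probably cluster in one arm.

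Intention to treat asks how everyone randomised to ketamine fared, including those who could not continue. If nobody observes the stopped participants, the mixed model fills the gap from their earlier scores and from those still being injected, in effect as if treatment had continued. The affected outcomes are MADRS (secondary, but the outcome on which section 12.3 bases the sample size) and opioid use (exploratory). The two primary outcomes concern feasibility.

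**Working it through.** **1. Which MADRS scores are lost.** Table 2 schedules MADRS at baseline, Tx2, Tx4, Tx6, Tx8 and three follow-ups. Section 10.6 puts clinical assessments before each injection.
- Stop at injection 1: only the baseline score remains.
- Stop at any of injections 1–7: the endpoint score is lost on all three endpoint readings.
- Stop at injection 8: the week-4 score is already taken, but a later endpoint is lost.
- Stops in Group B's optional ketamine phase come after week 4 and do not affect a week-4 comparison.

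**2. How many might meet the criterion.** Section 15.2 gives a rise in 29.8% of participants, with systolic 19.6 ± 12.8 and diastolic 13.4 ± 9.8 mmHg. Assumptions: ± is an SD, rises are normal, and the cited intravenous data carry over to 60 mg intramuscularly. For one session, before the repeat reading:
- Systolic: 1 − Φ((30 − 19.6)/12.8) = 0.208.
- Literal reading (the mean belongs to the 29.8% affected): 0.298 × 0.208 = 0.062, and × 15 = 0.9 participants.
- If the mean and SD describe everyone: 0.208 × 15 = 3.1. This is less natural, because it implies that Φ(19.6/12.8) = 94% had some rise.
- Diastolic: 1 − Φ((30 − 13.4)/9.8) = 0.045, adding at most 0.7 of 15, or 0.2 after multiplying by 0.298.
- Pulse: no data in the documents.

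The repeat reading lowers these figures and eight sessions can raise them. The documents give neither rate, so no trial-level figure is claimed.

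**3. Precision.** First, the plan's own figures. The mean of 7 measurements with AR(1) correlation 0.9 has variance factor 0.798.
- 15 per arm: 2.80 × 15.8 × √(0.798 × 2/15) = 14.4.
- 12 per arm: the same formula gives 16.1.

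Both match section 12.3. Now remove ketamine participants entirely, leaving m against 15. The detectable difference is 2.80 × 15.8 × √(0.798 × (1/m + 1/15)). Power at 14.4 is Φ(14.4/(15.8 × √(0.798 × (1/m + 1/15))) − 1.96).

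| Lost | m | Detectable difference | Power at 14.4 |
|---|---|---|---|
| 0 | 15 | 14.4 | 0.80 |
| 1 | 14 | 14.7 | 0.78 |
| 3 | 12 | 15.3 | 0.75 |

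Even three losses stay inside the plan's allowance for 20% dropout (16.1), although that allowance assumes equal loss in both arms.

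**4. Illustration of a one-sided shift (not an estimate).** Take 14.4 as the true effect. Suppose w of 15 are stopped and have lost a share s of it by the endpoint, while the model projects them as still treated. The overstatement is (w/15) × s × 14.4.
- w = 1, s = 0.5 to 1: 0.5 to 1.0 points.
- w = 3, s = 0.5 to 1: 1.4 to 2.9 points.

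Such a loss is plausible only for early stops. Section 2.0 reports: "The overall duration of anti-depressant response was found to last between 3-12 days". At two injections a week, injection 3 falls about 5 × 3.5 = 17.5 days before Tx8. Later stops would shift less, and so would the longer response (17 days on average) that section 2.0 cites for people with a family history of alcoholism.

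**5. Completion outcome.** A participant stopped at injection k who missed no visit has attended k + 1 of 12 visits. For k = 7 that is 8/12 = 67%, below the 75% threshold in section 12.2; for k = 8 it is 9/12 = 75%. If assessments continue and count, a stop at injection 1 followed by all seven remaining MADRS contacts gives (2 + 7)/12 = 75% and turns a non-completer into a completer. The fix has to prevent this.

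**The case against.** A reader might infer that section 10.6 breaches intention to treat. The documents do not support that. Intention to treat is stated as an analysis principle, section 10.6 moves nobody out of their randomised arm or out of the analysis set, and scores from before the stop stay in the mixed model, which is valid if the data are missing at random. What remains is narrower: the comparison is weakened because the endpoint of stopped participants is unobserved.

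The size may also be minor. On the literal reading of section 15.2, fewer than one of 15 meets the systolic criterion at one session, before the repeat reading. The matching illustration of 0.5 to 1.0 points is small beside a standard error of about 14.4/2.80 = 5.1. The 1.4 to 2.9 range needs three early stops and the less natural reading. This is a pilot with feasibility outcomes as primary. All of that stands and limits the weight of the point. It does not remove it, because outcomes never collected cannot be recovered at analysis.

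Finally, continued follow-up is not free. Table 2 schedules the Timeline Followback and drug screens at every treatment and follow-up visit, so keeping the full schedule after a stop at injection 1 would mean ten more visits. Telehealth is provided only for baseline (section 10.4) and follow-up visits (section 10.6). This objection stands, and the fix is confined to the MADRS time points for that reason.

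**Conclusion.** The concern holds as avoidable, arm-related missingness in the secondary MADRS outcome and the exploratory opioid-use outcome. It is worth correcting but does not threaten the trial.

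It rests on two inferences. Withdrawal from the study is taken to end assessment, because it is listed apart from stopping injections and nothing provides for follow-up. The loss is taken to fall mainly on ketamine, which is probable but unproven without a placebo rate.

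The number affected is unknown and may be about one of 15. Two stronger readings should be avoided. One is that the rule undermines power: the loss is from 0.80 to 0.78 for one participant or 0.75 for three. The other is that single-session rates can be compounded over eight sessions into a large number of withdrawals: the documents give neither the persistence after rest nor the correlation between sessions that this would need.

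**What to change.** - **Section 10.6:** keep the stopping criteria. Replace the second consequence, withdrawal from the study, with permanent discontinuation of study injections.
- **Follow-up after a stop in the randomised phase:** continue at least the remaining MADRS and Timeline Followback assessments at the Tx2, Tx4, Tx6 and Tx8 time points and the three follow-ups, unless consent is withdrawn. Amend the protocol to allow telehealth for these assessment-only contacts. Include the data in the mixed model.
- **Section 12.2:** add that visits attended after a section 10.6 stop do not count towards the 75% completion threshold, so that the second primary outcome stays as it is now. Report separately the number stopped and the randomised-phase injections received (of 8).

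Cost: up to seven contacts for a participant stopped at injection 1 and fewer for later stops, a short amendment, and two added lines in the report. No extra staff or procedures are needed.

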11.0 SPECIMEN COLLECTION AND BANKING

Data will be in the form of self-reported questionnaires, medical record review (including labs and pertinent medical history for the purpose of eligibility clarification), urine and breath samples, physical exam and electrocardiogram and structured clinical interviews conducted by the PI. This data will be obtained specifically for research purposes. No biologic specimens will be stored for future use. Serum based laboratory tests (complete blood counts, complete metabolic panels) and electrocardiograms will be conducted using MUSC's clinical laboratories with test results entered into the participant's electronic medical record.

12.0 DATA MANAGEMENT

12.1 Data Analysis Plan

Baseline demographic characteristics will be collected and descriptive statistics will be used to characterize participants. Data will be collected and managed using the secure REDCap (Research Electronic Data Capture) database. Descriptive statistics for primary outcomes will include 1) the percentage of individuals completing informed consent out of the number of individuals eligible on the

initial screening and 2) the percentage of individuals that complete informed consent which complete the full protocol. Other descriptive statistics for the sample population will be analyzed, and baseline characteristics that are found to be significantly associated with other outcome measures will be included as covariates. Spaghetti plots will be produced to guide modeling outcomes as a function of time. All analyses will be conducted based on intention to treat. Subjects assigned to Group B (placebo) who complete Study Wk4 (at which time main outcomes are assessed), may choose to receive 8 ketamine treatments before completing follow-up visits. To preserve study blinding, subjects who are among the final 6 subjects being enrolled will not be unblinded until primary outcomes are assessed for all 30 subjects.

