4.3 Exploratory Outcomes

Exploratory outcomes will include changes in characteristics related to opioid addiction including percentage of days using opioids and abstinence rates (Timeline Followback), motivation to quit (University of Rhode Island Change Assessment), craving for opioids (Visual Analog Scale), and related areas of psychiatric functioning.

- Timeline Follow-Back (TLFB; Sobell & Sobell, 1992): The TLFB obtains retrospective self-report of substance use by using a calendar and memory prompts to stimulate recall. Quantity and frequency assessments are made using this instrument (e.g., total amount of opioids used, percent of days using) as well as abstinence (yes/no). TLFB yields consistently high test-retest correlations and correlates well with other self-reports and collateral reports. The TLFB will assess consumption of opioids for 60 days prior to study entry, during the interventional phase and the follow-up phase. Use of nicotine and other drugs of abuse, including prescription drugs, will also be assessed using the TLFB.
- Urine Drug Screen (UDS) tests: Urine samples will be tested with a Multi-Drug Panel Test, which allows for the detection of THC/Marijuana, Cocaine, Phencyclidine, Opioids, Methamphetamines, Amphetamines, Barbiturates, and Benzodiazepines.
- Saliva Drug Screen tests: For follow-up visits conducted by telehealth, a Multi-Drug Panel saliva drug screen test may be optionally used in place of urine tests to facilitate ease of testing in a home setting.
- University of Rhode Island Change Assessment Scale (URICA; DiClemente & Hughes, 1999): This 32-item, self-reported questionnaire uses a five point Likert scale to assess levels of motivation to change according to the transtheoretical model (Precontemplation, Contemplation, Action, and Maintenance). This will be measured as the level of motivation to make changes may be mechanistically related to improving in opioid use.
- Visual Analog Craving Scale (VAS; McMillan & Gilmore-Thomas, 1996). At baseline, during the interventional visits, and at each follow-up visit, patients will be asked to report on the frequency, duration, and intensity of their opioid cravings on a 10 point (100 mm) VAS. This approach has been shown to yield a reliable and valid measure of craving in previous research.

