5.2 Inclusion Criteria

A subject may be eligible for enrollment if all of the following inclusion criteria apply within the thirty days prior to randomization:

- 1. Between the ages of 18 to 65 years old.
- 2. Able to provide informed consent.
- 3. Meet DSM-5 criteria for Major Depressive Disorder, without psychotic features.
- 4. Score at least 20 on the Montgomery-Asberg Depression Rating Scale.
- 5. Fulfill a minimum of 4 of 11 current opioid use disorder criteria by DSM-5.
- 6. Have used opioids illicitly at least once in the past month.
- 7. Subjects must be on a standard of care pharmacotherapy for OUD (buprenorphine, methadone or naltrexone) for at least one month.
- 8. Subjects taking other psychotropic medications (e.g. anti-depressants or non-benzodiazepine anxiolytics) must be maintained on a stable dose for at least four weeks before study initiation.
- 9. Must consent to random assignment to ketamine or placebo control.

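### Apart from antidepressant use, covariates are chosen by significance in about 30 patients, so each outcome's own baseline value may be left out of its model and available precision forgone

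*Combined protocol and SAP*

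**What the plan says.** Section 12.1 (Data Analysis Plan) sets the covariate rule: "baseline characteristics that are found to be significantly associated with other outcome measures will be included as covariates". It gives no candidate list, significance threshold, visit or reference outcome.

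Section 12.2 (Hypotheses for Analyses) lists the model terms as "intervention group (ketamine or placebo), time (number of days), and the interaction between the two". Of antidepressant use at baseline it says "this will be considered as an independent variable in the statistical analysis", so that variable is named before data are seen. It then adds: "In all of the analyses, covariates will be considered to examine mediations".

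Section 4.2 defines the MADRS outcome, "which will be calculated as a change from baseline to 4-week followup". Section 1.3 speaks of "repeated dependent measures of clinical outcomes at baseline and multiple time points after the first treatment". Neither section says whether baseline MADRS is a covariate, a row of the outcome vector, or only the subtrahend of a change score.

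The baseline data exist. Table 2 in Section 10.3 schedules the MADRS at baseline, and Section 4.3 states: "The TLFB will assess consumption of opioids for 60 days prior to study entry".

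**The concern.** The baseline value of an outcome is usually its best single predictor, and adjusting for it narrows the treatment comparison at no cost in patients. Under the rule in Section 12.1 it enters only if it happens to reach significance in about 30 patients. With a modest true correlation it will often fail, and if many baseline variables are screened, some with no real association will pass. The comparison affected is MADRS at one month, which Section 12.3 says the study is powered for. The percent-days-using-opioids analysis is affected in the same way.

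**Working it through.** **Inputs.** From Section 12.3: MADRS difference 14.4, SD 15.8, 15 per arm (12 after 20% dropout), 7 measurements, AR(1) correlation 0.9, significance level 0.05. Sidedness is not stated; two-sided is assumed. The baseline-to-one-month correlation ρ is not in the documents, so I show 0.30, 0.53 and 0.66. For reference, 0.9^6 = 0.53 and 0.9^4 = 0.66. The MADRS entry cut-off ("Score at least 20 on the Montgomery-Asberg Depression Rating Scale") may lower ρ by restricting range.

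**1. The plan's own figure.** The mean of 7 AR(1) measurements has variance factor 0.798, so the effective SD is 15.8 × √0.798 = 14.11.
- 15 per arm: (1.960 + 0.842) × 14.11 × √(2/15) = 14.44, against 14.4 stated.
- 12 per arm: 2.802 × 14.11 × √(2/12) = 16.14, against 16.1 stated.

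Both reproduce with no baseline term, so the stated 80% takes no credit for baseline adjustment.

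**2. One-month comparison, normal approximation.** Power = Φ(14.4 / (SD × √(2/15)) − 1.96), where √(2/15) = 0.365.
- Unadjusted: SD 15.8, power 70%.
- Baseline covariate: SD = 15.8 × √(1 − ρ²) = 15.07, 13.39, 11.93 for ρ = 0.30, 0.53, 0.656; power 74%, 84%, 91%.

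For opioid use (22 points, SD 25), power is 67% unadjusted, against 71%, 80% and 89% with a fixed baseline covariate at ρ = 0.30, 0.50 and 0.656.

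**3. Adding the screen.** These are simulated powers (t-based, so slightly lower than step 2) at 15 per arm for a single one-month visit. A candidate enters if p < 0.05 against the outcome. The ten-candidate case has one real baseline and nine noise variables; that count is an assumption.

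| Analysis | ρ = 0.30 | ρ = 0.53 | ρ = 0.66 |
|---|---|---|---|
| No covariate | 68% | 67% | 66% |
| Fixed baseline covariate | 70% | 80% | 88% |
| Screen, ten candidates | 64% | 75% | 85% |
| Screen, one candidate (fixed covariate in the same run: 69 / 79 / 88%) | 67% | 76% | 88% |

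The ten-candidate cost is 70 − 64 = 6, 80 − 75 = 5 and 88 − 85 = 3 points. The one-candidate cost is 2, 3 and 0 points; a separate run with 6,000 trials per cell gave 2.1, 2.7 and 0.7 at ρ = 0.30, 0.50 and 0.656. Repeat runs differ by about a point, so I quote about 1 to 3 and about 3 to 7. The fixed covariate gains 70 − 68 = 2 to 88 − 66 = 22 points over no adjustment. The screen misses the true baseline in about 70%, 20% and 5% of trials.

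**4. Type I error.** Null rejection under the screen was 4.5 to 5.2% with one candidate and 4.9 to 5.3% with ten.

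**5. The change score in Section 4.2.** SD of change = √(15.8² + b² − 2ρ × 15.8 × b), where b is the baseline SD (not given in the documents).
- b = 15.8: 18.69, 15.3, 13.11. Simulated power is 54 / 70 / 83%, clearly below the fixed covariate.
- b = 8: 15.42, 13.39, 12.16, close to the covariate SDs in step 2. Simulated power is about 70 / 81 / 88%, no material difference.

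With entry at 20 or more, a scale maximum of 60 and an assumed baseline mean of 34, the largest possible baseline SD is √((34 − 20) × (60 − 34)) = √364 = 19.1, reached only if every patient scores 20 or 60. A baseline SD near 15.8 is therefore hard to reconcile with the entry rule.

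**The case against.** Four readings go further than the documents allow.

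- A reader might infer that the stated 80% power is undermined. It is not: step 1 reproduces it without baseline adjustment.
- A reader might infer that screening is the only route into the model. Section 12.2 names antidepressant use in advance, and Section 12.1 does not say that nothing else may enter.
- A reader might infer that selection on outcome data inflates false positives. For the rule as written, simulated type I error stays near 5%. Inflation would need the analyst to choose among models after seeing the results, and nothing in the plan says this will happen.
- A reader might infer that the change score is always inferior. That depends on the baseline SD, and at about 8 the penalty disappears.

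The strongest defence is that baseline MADRS already enters the analysis, either through the change score or as a repeated measure. This stands in part: baseline is not ignored. But the plan does not say which applies, and an outcome row does not clearly solve the problem. With a free group term, the group-by-time interaction is still a change-score contrast, and the one-month contrast is essentially unadjusted.

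It is also fair that the candidate count is assumed, that with one candidate the cost is small, and that these figures describe a single visit, not the full mixed model. Finally, Section 4.1 makes feasibility primary, and efficacy is assessed only preliminarily.

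**Conclusion.** The point holds as a matter of efficiency and prespecification. The selection rule allows baseline MADRS and baseline opioid use to drop out of the models where they are most useful. No claimed power is lost and type I error is not at issue. The cost of the screen relative to a fixed baseline covariate is about 1 to 3 points of power with one candidate and about 3 to 7 with ten. This rests on a single one-month visit, a difference of 14.4, SD 15.8, 15 per arm and ρ between 0.30 and 0.66. The gain of the fixed covariate over no adjustment runs from about 2 to 22 points, depending almost wholly on ρ. Importance is low to moderate, because Section 4.2 makes MADRS secondary and Section 4.3 makes opioid use exploratory.

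**What to change.** Replace the selection sentence in Section 12.1 with:

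*The MADRS model includes baseline MADRS, and the percent-days model includes baseline percent days using opioids (60-day TLFB), as fixed covariates, with post-baseline values as the outcome rows; both include baseline antidepressant use. No covariate for the treatment comparison is selected by significance testing on outcome data.*

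In Section 12.2, limit the sentence on considering covariates to exploratory mediation analyses. Otherwise the discretion removed from Section 12.1 remains there.

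Section 4.2 can still report change from baseline: at a given visit, once baseline is a covariate, the estimated treatment difference is the same for change as for the post-baseline value.

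The cost is two short text edits. Every variable is already collected, and no patient, visit or assessment is added.
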